## Background

Dental implants have traditionally been placed in a two stage surgical procedure. Initially, the implant body is placed, followed by three to six months later for the connection of the implant to the abutment. The implant is finally loaded when a prosthetic restoration is affixed to the abutment. Today, evidence exists which reveals that immediately loaded implants may have survival rates that are equal to those of implants loaded after a time delay. Mijiritsky et al. (2009) showed a survival rate of non-functional immediately loaded implants of 95.8%. The amount of dimensional changes of the soft tissues, however, has been poorly documented in the literature. A study by Cardaropoli et al. (2006) evaluated peri-implant tissue alterations in the maxillary anterior region and found 0.6mm apical displacement of labial tissues. However, their approach employed the two stage surgical procedure. Therefore, many questions remain in regard to the clinical success of immediately loaded implants. Following tooth extraction, the alveolar ridge undergoes remodeling of the buccal and lingual walls of the extraction socket, with more pronounced bone loss on the buccal aspect. The placement of an implant into a fresh extraction site does not prevent bone remodeling (Araujo, 2005), and therefore, these ridge alterations must be considered when placing immediate implants, especially in the esthetic zone. After installation of implants into fresh extraction sockets, marginal circumferential defects of varying sizes usually exist.

Whether complete bone fill may occur, regardless of the size of the gap distance between the buccal plate and implant, is still a question to be answered. Botticelli et al. (2004) found that marginal gaps of 3.4 mm can heal with substantial bone formation without the use of barrier membranes or filler materials. Also, a convex surface such as a properly designed provisional restoration provides a template against which soft tissue can heal and remodel (Weinlander, 2010). Ideally, it will allow for adequate bulk of tissue formation and proper emergence profile while meeting esthetic demands and protecting any graft material placed in the gap. Studies have also addressed the effect of gingival biotype on hard and soft issues in immediate extraction implant procedures in the esthetic zone (Kois, 2001, Kan, 2011). Kan (2011) reported apicoocclusal facial gingival tissue stability following immediate implant placement in the maxillary esthetic zone without guided bone regeneration, favorable success rates and periimplant tissue responses. Although this study reported spontaneous interproximal papilla regeneration, there was however, continued overall facial recession, more so in the thin soft tissue biotype than the thick tissue biotype. Raes at el. (2011) reported successful results and less vertical recession of the facial gingival with a flapless surgical approach during immediate implant placement in thick biotype cases where the bony walls are intact and proper treatment planning with diagnostic tools is executed in appropriate cases. It is a challenge to measure changes in soft tissue width because this dimension is difficult to assess and reproduce. Windlisch et al. (2007) described a new method to measure intra-oral volume changes based upon an optical system which scans the intraoral anatomy with a camera (Schneider, 2003.) In an in vitro study, several datasets of 3-D objects were captured and volumetric differences measured. The results were highly accurate and reproducible. The same method was reported by Strebel et al. (2009) and Schneider et al. (2010) to measure soft tissue changes of the dental papilla, alveolar ridge and buccal mucosa. In a recent study by Thoma et al. (2010), soft tissue

volume gain with a newly developed collagen matrix was evaluated in chronic ridge defects compared to sub-epithelial connective tissue grafts in dogs. Casts were obtained and soft tissue changes were digitally analyzed. The aim of the current study is to evaluate the soft tissue dimensional changes after extraction of teeth in the esthetic zone, when combined with the placement of implants into these fresh extraction sockets. Furthermore, the effect of placing a graft material, Bio-OSS Collagen®, into the gap between the 3i® implant and the labial plate of bone will be evaluated after an immediately loaded provisional restoration is placed.

# **Study Design**

This is a single-blind, randomized, controlled, single-center study:

32 subjects will have an immediate implant placed in the maxillary anterior region (#4-12) after extraction of a hopeless tooth. 16 subjects will be randomly selected to receive Bio-Oss Collagen® (Test group) and 16 subjects will have no graft (Control group) in the gap between the implant and the labial plate of bone.

Hopeless maxillary anterior teeth will be extracted and implants will be placed in a flapless procedure. Implants will be immediately loaded with provisional restorations once determined that the implant is stable. Changes in vertical height and horizontal dimensional changes of the free gingival margins will be evaluated at 3, 6, and 12 months post-immediate implant placement. Both groups are only different by the draft that will be placed at the time of implant placement. Both treatment choices are currently standard of care in immediate implant therapy. Patients will only be include into the study if the extraction socket is intact as outlined below and, therefore, immediate implant placement with or without drafting would be possible. If patients decide not to go ahead with the study, treatment could be performed either way in our clinic. Both methods are standard of care.

Based on the literature (see above and here):

Immediate implant placement can be done with or without grafting. An intact socket does not necessarily require grafting. Currently, both procedures (placement with grafting and without grafting) are considered standard of care). One group will receive grafting and the other group

will receive no grafting. Whether the patient can really participate in the study can only be decided after the socket has been evaluated and has been classified as intact (no buccal bone loss, no dehisced bone). Nevertheless, patients will sign study consent before the surgical treatment at the time of initial consultation. If the socket has been compromised during extraction and an immediate implant placement will not be possible, patient will not proceed with study implant therapy and will continue his treatment in the clinic. A standard of care treatment would be to place a delayed implant at a later time point. There is no risk involved in participating in the study since both treatment choices are standard of care.

## **Statistical Procedures**

Our current study aims to analyze dimensional stability after immediate implant placement in fresh extraction sockets. We will simultaneously graft the socket with a synthetic combination bone material and compare it to sockets that will not be grafted. Currently, there are no randomized controlled clinical studies available that compare these two different treatment modalities. However, we will use a randomized controlled study that compared different socket /implant treatments (immediate versus delayed implant placement). They found a difference in buccal/lingual dimensional stability (1.9 in an immediate group versus 3.06 in a delayed group) (Covani et al, 2004). In order to detect a difference of 10% with a power of 80% at a significance level of 0.05 between control and study group, we will need to perform at least 16 procedures per group. Primary efficacy variable is the height and thickness of keratinized tissue at 3,6,12, 24 months post surgery. Post surgery assessment of recession width, color, texture and contour ratings, marginal gingival level, biotype assessment are secondary variables. Summary statistics (mean, SD, median, p25, p75, min, max) will be calculated for all measured variables in each group. Results between both groups will be compared using the Student's t-test for normal distribution and the Mann- Whitney-U test for a non-parametric distribution of values. Categorical values will be compared using the chi-square test. For secondary analyses, we will use appropriate parametric or nonparametric tests to compare group differences.

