- 12. Subject will be seen at 3,6 and 12 months. At each of these visits, alginate impressions will be taken and digitally scanned and analyzed. At 6 months, periapical film will be taken and pick-up impression with open tray impression coping.
- 13. Deliver screw retained final restoration with zirconia framework and pressed lithium disilicate.
- 14. Take 6th alginate impression. At one year (6 months after delivery of final restoration.) Measure Vertical height of free gingival margin from MGJ Visits 1, 2, 4-6. Measure horizontal dimensional change to tenth of mm using calipers 1mm, 2mm below gingival margin at Visits 1, 2, 4-7.

- 15. All models created from alginates will be poured with Whip Mix labstone. All models used for fabrication of the final crown will be poured in silky Rock (Whip Mix) or Resin Rock (Whip Mix).
- 16. Measurements will be done by scanning the facial tissues on each model and then superimposing them on the original one. The difference in height (wKT) and facial-lingual dimension (thickness or tKT) of the free gingival will be evaluated at 3, 6 and 12 months.
- 17. The cast that was used for the final crown will be evaluated for facial thickness of tissue by measuring one mm and 2mm below the margin of the free gingiva.
- 18. Images of the implant crown, the surrounding gum tissue and the neighboring teeth will be shown to people outside of the study and they will be asked to rate the color change of the gum tissue.
- 19. De-identified data will be transferred from Columbia to Jena University. Transfer will be done using an encrypted external device. Data will be stored on a desktop computer at Jena University. The computer is password protected.

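### The 0.05 level and 80% power with 16 per group apply to one comparison, but the primary variable holds six to eight and no rule says which decides

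*Combined protocol and SAP*

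**What the plan says.** Statistical Procedures gives one power statement: "In order to detect a difference of 10% with a power of 80% at a significance level of 0.05 between control and study group", from which "we will need to perform at least 16 procedures per group". It ties this to no measure and no visit. The only prior data offered are from a study of immediate versus delayed implants: "They found a difference in buccal/lingual dimensional stability (1.9 in an immediate group versus 3.06 in a delayed group". No standard deviation is given.

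The same section then states: "Primary efficacy variable is the height and thickness of keratinized tissue at 3,6,12, 24 months post surgery". For the analysis, "Results between both groups will be compared using the" t-test or, for non-normal data, the Mann-Whitney test.

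The times differ elsewhere. Study Design has "Changes in vertical height and horizontal dimensional changes of the free gingival margins will be evaluated at 3, 6, and 12 months", and Study Procedures, item 16, has "The difference in height (wKT) and facial-lingual dimension (thickness or tKT) of the free gingival will be evaluated at 3, 6 and 12 months". Neither schedules 24 months.

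Thickness also has two possible methods. Item 16 takes it from superimposed scans of the models, while item 14 says "Measure horizontal dimensional change to tenth of mm using calipers 1mm, 2mm below gingival margin".

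**The concern.** A significance level and a power describe a specific test or a specific decision rule. Here they are attached to a single difference, while the primary variable is a set of differences, each open to its own two-group test. The documents do not say whether one significant result is enough, whether all are needed, or which comes first.

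Two things are at stake. A difference seen in one comparison only, such as height at 3 months, could be reported as the primary result at more than the stated 5% risk of a false positive. And a mixed result, such as thickness significant and height not, has no reading fixed in advance. The justification for 32 patients covers only one of the comparisons that could be put forward.

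**Working it through.** **Inputs from the plan.** Level 0.05, power 80%, 16 per group, 1:1 allocation, two-group t-test. Not given: sidedness (two-sided assumed), the standard deviation (SD), the base of the 10%, and the correlations among the outcomes (assumed, with a range).

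**1. Count.** As written in Statistical Procedures: 2 measures × 4 times = 8. At the times in Study Design and item 16: 2 × 3 = 6. The smaller count is used below.

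**2. The plan's own figure.** Without an SD, 16 cannot be reproduced, so it is solved backwards. By normal approximation, d = (1.960 + 0.842) × √(2/16) = 0.99 SD. By the noncentral t-test, d = 1.024 SD. In the units of the cited values, with the t-test:

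- 10% of 1.9 implies an SD of 0.19/1.024 = 0.19
- 10% of 3.06 implies an SD of 0.306/1.024 = 0.30
- the full difference of 1.16 implies an SD of 1.16/1.024 = 1.13

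The plan does not say which was meant. From here 16 per group is taken at face value: one comparison has exactly 80% power at 0.05 when the true difference is 1.024 SD.

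**3. If any comparison may count, each at 0.05.** Under independence the error is 1 − 0.95^k: 9.75% for k = 2, 26.5% for k = 6, 33.7% for k = 8. Measurements on one patient are likely to be positively correlated, so t-tests with 16 per group and equal correlation ρ were simulated.

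**4. If all six must be significant at 0.05.** Under independence, power is 0.80^6 = 26%. The correlated cases come from the same kind of simulation, with a true difference of 1.024 SD on every outcome.

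| ρ (assumed) | Any of six: false-positive chance | All six: power |
|---|---|---|
| 0 | 26.5% | 26% |
| 0.5 | 21% | 47% |
| 0.8 | 14% | 61% |
| 0.9 | 11% | 67% |
| 0.95 | 9% | 71% |

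**5. If 0.05 is split equally (Bonferroni).** Power per comparison at 1.024 SD with 16 per group:

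| Comparisons | Level each | Power each | Per group for 80% |
|---|---|---|---|
| 1 | 0.05 | 80% | 16 |
| 2 | 0.025 | 70% | 20 |
| 6 | 0.0083 | 54% | 25 |
| 8 | 0.00625 | 49% | 27 |

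**6. One named comparison.** Level 0.05 and 80% power at 1.024 SD with 16 per group: unchanged.

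**The case against.** The strongest reply is that the plan never adopts an any-of-six rule. Height and thickness could mean that both are required, and a rule requiring every comparison does not inflate the error. Repeated measures at one site are also likely to be strongly correlated, which brings the error under an any-of-six rule down to about 9% at a correlation of 0.95. If the graft acts on all six outcomes, at least one Bonferroni test succeeds in 89%, 77% and 70% of trials at correlations of 0.5, 0.8 and 0.9. All of this is fair, and it limits the size of the problem. It does not remove it. At every correlation tried, the error stays above 5% if any one counts and the power stays below 80% if all must, and the plan does not say which applies.

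It could also be said that thickness at 12 months is plainly the intended primary. The documents do not support that. Height is listed first, and 24 months is the last time listed. The cited buccal/lingual contrast is not identified as keratinized-tissue thickness and comes from a different comparison of treatments.

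Three stronger readings are tempting:

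- A reader might take 26.5% (or 33.7% for eight) as the trial's actual error rate. These figures need independence, which is implausible here, and a success rule that the plan does not state.
- A reader might count nine comparisons by adding the two caliper depths. That assumes height and caliper thickness share the same three times. Item 14 gives them different visit lists (1, 2, 4-6 and 1, 2, 4-7), with no key from visits to months.
- A reader might conclude that 16 per group is wrong. It is not shown to be. A difference of 1 SD gives 2 × (1.960 + 0.842)² = 15.7, so 16, by normal approximation (78% power by the t-test). The missing SD and the undefined base of the 10% are a separate reporting gap.

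**Conclusion.** The point holds. The stated 0.05 and 80% are valid for one comparison, and the plan does not identify it. With six comparisons:

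- the false-positive chance is about 9% to 21% if any one counts
- power is 54% for each comparison if the level is split
- power is about 47% to 71% if all must be significant

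The ranges are for assumed equal correlations of 0.95 to 0.5. Independence gives the outer values of 26.5% error and 26% power. All figures assume two-sided tests, normal data and 16 evaluable patients per group, and the power figures also assume a true difference of 1.02 SD. That the plan lacks a deciding rule rests on none of these assumptions. The defect affects how the main result may be read and can be repaired before analysis, so it should be fixed; it does not invalidate the design.

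**What to change.** 1. Reconcile the 24-month time in Statistical Procedures with the 3, 6 and 12 months in Study Design and Study Procedures, and map the visit numbers in item 14 to months.
2. Before analysis, name one primary comparison, tested two-sided at 0.05: one measure (height or thickness), one method (superimposed scan as in item 16, or caliper at a stated depth as in item 14), and one time at which that measure is scheduled. The final evaluated time is a natural choice. Thickness is a reasonable option given the buccal/lingual contrast cited for sample size, but the choice is the investigators'.
3. If the other measure must also be confirmatory, test it at the same time at 0.05 only if the first is significant. This fixed sequence keeps the overall error at 5% and costs the first test no power.
4. Make all other measures and times secondary, with confidence intervals. This includes 24 months if it is kept and not chosen.
5. Tie the power statement to the named comparison, with a sourced SD and the reference value for the 10%. If no SD can be sourced, state that 16 per group has 80% power for a difference of 1.02 SD (two-sided t-test). That reports what the trial can detect; it does not justify the number.

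The cost is a paragraph of wording and a search for one SD. Naming the comparison adds no visits, and the number of patients changes only if a sourced SD shows 16 per group to be too few. The downside is that an effect seen only in the other measure, or at another time, counts as secondary evidence.

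### The claim that 16 per group gives 80% power for a 10% difference is unsupported: the design detects about 1.02 SD, for a comparison the plan never names

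*Combined protocol and SAP*

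**What the plan says.** The justification is in Statistical Procedures. It notes that no randomised trial has compared grafting with no grafting, and turns instead to a trial of immediate versus delayed placement, which reported "1.9 in an immediate group versus 3.06 in a delayed group" for buccal/lingual dimensional stability. The target is then set in these words: "In order to detect a difference of 10% with a power of 80% at a significance level of 0.05 between control and study group". The size said to follow from that target is given in the same sentence: "we will need to perform at least 16 procedures per group".

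The outcome is then defined: "Primary efficacy variable is the height and thickness of keratinized tissue at 3,6,12, 24 months post surgery". Groups are to be compared with the "t-test for normal distribution and the Mann- Whitney-U test for a non-parametric distribution of values". No adjustment for multiple comparisons is stated.

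Two other sections give a shorter schedule. Study Design says "Changes in vertical height and horizontal dimensional changes of the free gingival margins will be evaluated at 3, 6, and 12 months", and Study Procedures, describing the superimposed model scans, says "The difference in height (wKT) and facial-lingual dimension (thickness or tKT) of the free gingival will be evaluated at 3, 6 and 12 months". Neither mentions month 24.

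**The concern.** A sample size for comparing two means needs a difference and an SD in the same units. The plan gives a percentage without its base and no SD. SD appears only as a descriptive statistic to be reported. The step from 1.9 versus 3.06 to 10%, and from 10% to 16, is not shown, and no other section supplies it.

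This sentence is the only statistical basis for 32 subjects. As it stands, a reader cannot tell what difference the trial can detect, and might take a non-significant result as evidence against a 10% difference. The 80% and 0.05 describe one test, while the primary variable covers two dimensions at several visits.

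**Working it through.** **Inputs.** From Statistical Procedures: alpha 0.05, power 80%, difference 10% (base not stated), cited means 1.9 and 3.06, 16 per group, t-test or Mann-Whitney. From Study Design: 16 versus 16. Not stated: SD, sidedness, dropout. Two-sided testing is assumed unless noted.

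**1. Can 16 be reproduced?** Not from the stated inputs. The normal formula is n per group = 2(1.960 + 0.842)² / d², where d = difference/SD. With d = 1, n = 15.7, which rounds up to 16. So an SD equal to 10% of the base would give the plan's figure. The t-test gives 16.7 in that case, and power with 16 is 78%.

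**2. What 16 per group detects at 80% power (one comparison).**
- Normal approximation: 2.802 × √(2/16) = 0.99 SD.
- Two-sided t-test (noncentral t): 1.024 SD.
- One-sided t-test: 0.90 SD.
- Mann-Whitney under normality: 1.024/√0.955 = 1.05 SD.

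With the two-sided t-test, a 10% difference therefore has 80% power only if the SD is at most 10/1.024 = 9.8% of the base. If the SD were 20% of the base (assumption), power would be 28% and 64 per group would be needed.

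**3. Do the cited figures lead to 10%?** 3.06 − 1.9 = 1.16. This is 1.16/3.06 = 38% or 1.16/1.9 = 61%.

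**4. Can one SD connect both the 10% and the 1.16 gap to 16?** Dividing each difference by 1.024 gives the SD at which 16 per group has 80% power:

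| Reading | Difference | SD implied by 16 | Consequence for the other reading |
|---|---|---|---|
| 10% of 1.9 | 0.19 | 0.186 | 1.16 would need 2 per group (power 86%) |
| 10% of 3.06 | 0.306 | 0.299 | 1.16 would need 3 per group (power 94%) |
| The cited gap | 1.16 | 1.133 | 0.19 has 7.4% power and 0.306 has 11.5%; about 560 or 217 per group needed |

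The average of the two means, 2.48, gives an SD of 0.242, between the first two rows. The two readings coincide only if 10% of the base is 1.16, that is, a base of 1.16/0.10 = 11.6. No such base appears in the documents. Reading the 10% as a difference in proportions does not give 16 either: at least 74 per group would be needed.

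**5. How many primary comparisons?** Two dimensions × four visits = 8 as Statistical Procedures is written. With only the 3, 6 and 12 month visits of the other two sections, 2 × 3 = 6. For independent tests, the chance of at least one false positive is 1 − 0.95⁸ = 34% or 1 − 0.95⁶ = 26%. Simulated t-tests with 16 per group and no true effect agree for independent measures (33% to 34% for eight tests, 26% to 27% for six). With an assumed correlation of 0.9 between visits and 0.5 between dimensions, they give about 16% to 17% for eight and 15% for six.

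**6. Detectable difference under variants.** Alpha split over height and thickness (0.025 each): 1.14 SD. One comparison with 14 evaluable per group (assumption): 1.10 SD.

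**The case against.** The strongest reply is that 16 may be right. A standardised difference of 1 gives 15.7, so the authors may have taken an SD of about 10% of the mean, perhaps from the cited trial, and quoted 1.9 versus 3.06 only as context. The plan never says that 16 follows from both the 1.16 gap and the 10%. This stands, and it limits the point to a claim that the documents do not support.

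Three stronger readings are tempting, and the documents do not bear them out:
- *The power claim is false, or the trial is underpowered for 10%.* This cannot be shown without the SD and the base, and neither is given.
- *True power is 7% or 11%.* Those figures use an SD solved backwards from one possible derivation of 16. They show that the readings disagree; they do not measure this trial's power.
- *No SD could reconcile the inputs.* This holds if the 10% is of 1.9, 3.06 or their average. A base of about 11.6, such as some larger ridge dimension, would reconcile them, although none is stated.

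It can also be said that the planned group means and SDs allow intervals to be calculated afterwards, and that the plan admits there was no prior trial of this comparison. Both are fair. Neither supplies the missing inputs, or says which of the primary tests the 80% refers to.

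**Conclusion.** The point holds in this limited form and should be fixed. The 10% claim does not follow from the inputs cited for it, and its SD and base are missing. The figure that can be stated is 1.02 SD at 80% power, assuming a two-sided t-test, one comparison and all 32 subjects evaluable. A 10% difference is within reach only if the SD is no more than about 9.8% of an unstated base.

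The power and the 0.05 belong to no named comparison. Followed as written, the plan runs eight unadjusted primary tests (six if month 24 is not measured). The false-positive range rests on the assumed correlations, and it would remain even if the missing SD were supplied.

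**What to change.** 1. Name one primary dimension (height or thickness), as change from the original model, at one visit common to all three sections, for example 12 months. Make the other dimension and visits secondary. Alternatively, keep both dimensions at that one visit and split alpha.
2. Reconcile month 24 in Statistical Procedures with the 3, 6 and 12 month schedule in Study Design and Study Procedures.
3. Replace the 10% sentence with: *16 per group gives 80% power (two-sided 0.05, t-test) to detect 1.02 SD in [that variable].* Use 1.14 SD if alpha is split. If some loss is expected, give that figure too, for example 1.10 SD for one comparison with an assumed 14 evaluable per group.
4. State why a difference of that size matters, or that the size is fixed at 32 for feasibility.
5. Keep 10% only with a stated base and a sourced mean and SD, and recompute n from them. Do not present 1.9 versus 3.06 as its basis.

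The cost is wording, with no extra patients. The downside is a less favourable stated figure and the move of one dimension or several visits to secondary status. If 10% is kept as the target, the recomputed size could be larger: 64 per group at an assumed SD of 20% of the base.

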# **Study Procedures**

At the present time, grafting or no grafting at the time of implant placement can be considered standard of care. We will take measurements to compare both groups. How measurements are taken is outlined below:

The surgical technique is described as:

- 1. Administration of 2000mg Amoxicillin-1 hour prior to surgery. For patients allergic to Amoxicillin, 600mg Clindamycin 1 hour prior to surgery will be substituted.
- 2. Administration of local anesthesia and impression using alginate will be taken to measure ridge dimensions.
- 3. Extraction of hopeless tooth will be performed without a flap. Dental extractions are usually done without raising a flap. Only if the tooth is very compromised and the tooth is difficult to access, a flap needs to be raised. Extraction sockets will be evaluated to determine whether it is intact and has no lesion or shows signs of bone loss. This can be done using a periodontal probe. Dental implants will only be placed if the socket is intact.
- 4. Check for labial plate of bone that is <4mm from the gingival margin.
- 5. Placement of implant into socket towards palatal wall.
- 6. Measure:
  - a. Thickness of buccal plate 1 mm from crest with special calipers.
  - b. Distance from buccal of implant to buccal crest of bone (horizontal gap distance).
  - c. Vertical depth of gap on facial aspect of implant
  - d. 16 subjects will randomly get Bio-OSS Collagen® packed firmly into gap.
- 7. Place temporary abutment and fabricated screw-retained provisional.
- 8. No sutures will be used since no flap was raised. However, if at the surgeon's discretion sutures were indicated, they will be placed. An X-ray will be taken after implant placement. This is standard of care. However, a half arch alginate impression will be taken and attached to the rim that is being used to hold the X-ray film. This way the patient will always bite down in the same way and the X-ray will always be shot in the same angulation.
- 9. Take 2nd alginate impression:
- 10. Placement of subject on appropriate analgesic (i.e. Acetominophen with or without codeine #3 or #4, or Motrin 600mg, or Vicodin 500/5/1-2 tabs q6h prn. Rinses with 0.12% Chlorhexidine Gluconate BID for 14 days.
- 11. Subject will be seen at 1 week post op.

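### Biotype is named only as a post-surgery outcome, so the trial cannot stratify on it, check its balance or adjust for it, although the Background links thin biotype to more recession

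*Combined protocol and SAP*

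**What the plan says.** The Background describes a study of immediate implants in the maxillary esthetic zone that found "continued overall facial recession, more so in the thin soft tissue biotype than the thick tissue biotype". It also reports good flapless results in thick-biotype cases. This trial works in the same setting: immediate, flapless, anterior maxilla.

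Statistical Procedures gives biotype one role: "Post surgery assessment of recession width, color, texture and contour ratings, marginal gingival level, biotype assessment are secondary variables". The primary variable in the same section is the height and thickness of keratinized tissue. The arms are to be compared by Student's t-test or the Mann-Whitney U test, and no covariate is named.

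On allocation, Study Design says "16 subjects will be randomly selected to receive Bio-Oss Collagen® (Test group) and 16 subjects will have no graft (Control group", with no stratification factor, blocking or minimisation. Study Procedures lists the graft as step 6d: "16 subjects will randomly get Bio-OSS Collagen® packed firmly into gap".

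Some related baseline data are planned in Study Procedures:

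- Step 2, before extraction: "Administration of local anesthesia and impression using alginate will be taken to measure ridge dimensions".
- Step 6a, listed before the graft: "Thickness of buccal plate 1 mm from crest with special calipers". Steps 6b and 6c add the horizontal and vertical gap.
- Step 16: "Measurements will be done by scanning the facial tissues on each model and then superimposing them on the original one".

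None of these is called biotype, and none is given a part in allocation or in the comparison of arms. The Inclusion Criteria set no biotype limit.

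**The concern.** The plan cites biotype as related to recession, admits both types and then first reads biotype after treatment. Tissue thickness is part of the primary variable. A biotype reading taken once the gap has been grafted or left empty may therefore partly reflect the graft, and it cannot stand in for a baseline value.

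Two things are at stake. With 32 subjects, a chance excess of thin sites in one arm could move the observed difference, and the trial would hold no biotype record with which to see or correct this. Precision that a baseline covariate might give is also left unused. A pre-extraction biotype reading cannot be taken once the tooth is out.

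**Working it through.** **1. The plan's own figure.** Statistical Procedures states 16 per group for a 10% difference, 80% power and a 0.05 significance level. It gives no SD and no base for the 10%, so 16 can be neither confirmed nor refuted. Taken two-sided, n = 16 per arm corresponds to a standardised effect of √(2/16) × (1.960 + 0.842) = 0.99 by the normal formula, or 1.02 by the t distribution. Steps 2 to 4 do not depend on the 16 being justified, only on its being the arm size. Step 5 uses the 1.02 as a starting point.

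**2. Where biotype could enter.** I looked at four places:

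- Eligibility (Inclusion Criteria): not restricted.
- Measurements before the graft step (Study Procedures, steps 1 to 6c): ridge impression, socket check, buccal plate thickness and gap. Biotype is not among them.
- Allocation (Study Design): 16 and 16, no factor named.
- Analysis (Statistical Procedures): two-group tests, no covariate.

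A chance imbalance is therefore handled neither in the design nor in the analysis.

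**3. How often chance imbalance occurs.** Inputs: 16 per arm (documents); prevalence p of thin biotype 20-50% (assumed, because the documents give none). Let X and Y be the numbers of thin subjects in the two arms, independent Binomial(16, p). Then P(|X − Y| ≥ 4) is the sum of P(X = i) × P(Y = j) over all i, j with |i − j| ≥ 4. The SD of the difference in proportions is √(2p(1 − p)/16).

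| p | SD of difference in proportions | P(arms differ by 4 or more) |
|---|---|---|
| 20% | 0.141 | 11.9% |
| 30% | 0.162 | 17.5% |
| 40% | 0.173 | 20.6% |
| 50% | 0.177 | 21.5% |

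The range is about 12-22%. A calculation that fixes the total number of thin subjects is sensitive to whether that total is odd or even. With exactly 16 thin of 32 the hypergeometric probability is 28.9%, but with 15 or 17 it is 15.6%. With exactly 8 it is 22.0%, but with 7 it is 8.3% and with 9 it is 11.3%. The total is not known in advance, so the binomial figures are the ones to use.

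**4. What an imbalance does.** Let D be the thin-thick gap in mean outcome. A difference of 4 thin subjects shifts the unadjusted arm difference by (4/16) × D = 0.25 D. The documents give no D. For illustration:

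- D = 0.25 mm: shift 0.06 mm
- D = 0.5 mm: shift 0.125 mm
- D = 1.0 mm: shift 0.25 mm

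The only recession figure in the Background is 0.6 mm of labial displacement in a two-stage study. That is a total, not a thin-thick gap, and it makes the upper values of D look high.

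**5. What adjustment might gain.** Suppose the unadjusted test truly had 80% power (standardised effect 1.02), and the baseline covariate explains a share R² of outcome variance (assumed). The residual SD is multiplied by √(1 − R²), so the effect becomes 1.02/√(1 − R²):

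- R² = 0.1: effect 1.08, power about 84%
- R² = 0.2: effect 1.14, power about 88%
- R² = 0.3: effect 1.22, power about 92%

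If the covariates explained nothing, falling from 30 to 28 residual degrees of freedom would lower power from 80.0% to 79.8%.

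**The case against.** The strongest reply is that randomisation balances biotype in expectation whether or not anyone measures it. The unadjusted t-test remains valid, because chance imbalance is already part of the error that its p-value reflects. This stands. A reader might infer that allocation cannot balance biotype or that the comparison is biased. The documents support neither. What is lost is stratification, a balance check and adjustment.

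Four further points stand in whole or in part.

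- A reader might take biotype to be the main driver of recession. The Background says only that recession was greater in thin biotype. It also discusses buccal bone remodelling and gap size, and the plan does measure buccal plate thickness and the gap.
- A reader might fear that adjusting for post-surgery biotype would remove part of a graft effect. The plan proposes no such adjustment and no biotype subgroup. It lists biotype as an outcome, which is a proper role for a reading taken then.
- The shift in millimetres should not be set against the 10% target. The cited biotype relation is about facial recession, which is vertical. The planning means (1.9 and 3.06) are buccal/lingual, and neither their unit nor the base of the 10% is stated.
- The sentence listing the secondary variables is loosely worded, and the available text ends at the inclusion criteria. An unlisted baseline reading, or a biotype limit elsewhere, cannot be fully excluded. If either exists, the statistical section should say so.

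The pre-extraction cast and buccal plate thickness carry some baseline information, but the plan gives neither a role in allocation or analysis. They soften the point without removing it.

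**Conclusion.** The point holds as a gap in precision and in protection against chance imbalance, not as a source of systematic bias. The plan attaches prognostic weight to biotype but describes no baseline reading of it and no use of it in allocation or analysis. At 16 per arm, a difference of 4 or more thin subjects has a probability of about 12-22%, if thin prevalence is 20-50%. It would move the unadjusted difference by a quarter of a thin-thick gap that the documents do not give. The possible gain in power depends on an assumed R², and the documents cannot say how much of the variation in height or thickness biotype explains. The trial is valid without the change. The change is worth making because it is cheap and cannot be made later for subjects already treated.

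**What to change.** 1. In Study Procedures, add a biotype reading (thin or thick) by a defined method, for example with the periodontal probe, before extraction and before allocation. Say at which visit it is taken, since the available text numbers visits without defining them.
2. In Statistical Procedures, make the between-arm comparison of the primary variable an ANCOVA, with baseline biotype and the baseline tissue dimension from the pre-extraction cast as prespecified covariates. Tabulate baseline biotype by arm.
3. Stratified allocation by biotype is an option, but only with concealed lists and varying block sizes. The trial is single-blind and the surgeon sees whether a graft is placed, so small fixed blocks within two strata would make later allocations guessable. The covariate approach avoids that risk.
4. Keep any post-surgery biotype reading as an outcome only, and state that it will not be used as a covariate or subgroup factor.

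The cost is one extra probe reading per subject and one or two degrees of freedom. If allocation is stratified, arm sizes may also end slightly unequal.
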